- Prevaccination blood samples for immunogenicity will be drawn from maternal participants in Phase 2 only.
- The investigator and site staff will ensure the active elicitation and collection of AEs and SAEs through 1 month after Vaccination 2. From 1 month after Vaccination 2 until the 6-month postdelivery follow-up, SAEs will be collected.

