8.11.1.1. Visit 2 – Vaccination 2 (Clinic: 19-23 Days After Vaccination 1)

If delivery occurs before this visit, this visit will be conducted as soon as possible after delivery. It is anticipated that the procedures below will be conducted in a stepwise manner; ensure that procedures listed prior to administration of the vaccine are conducted prior to vaccination.

- Measure vital signs (body temperature, pulse rate, and seated blood pressure).
- Perform targeted physical examination evaluating/noting any clinically significant abnormalities within the following body systems: general appearance; skin; head, eyes, ears, nose, and throat; heart; lungs; abdomen; musculoskeletal; extremities; neurological; and lymph nodes. Significant medical and surgical history and abnormal observations from the physical examination will be documented and recorded in the CRF.
- Perform obstetric examination including but not limited to fetal heart tones and fetal movement.
- Record AEs and SAEs as described in [Section 8.3](#).
- Review the participant's reactogenicity e-diary data. Collect stop dates of any reactogenicity e-diary events ongoing on the last day that the reactogenicity e-diary was completed and record stop dates in the CRF if required.
- Record nonstudy vaccinations as described in [Section 6.5](#).
- Collect and record concomitant medication associated with AE/SAEs.
- Ensure and document that the participant is still eligible for continued participation.
- Ensure that the maternal participant meets none of the temporary delay criteria as described in [Section 5.5](#).
- Collect a blood sample (approximately 20 mL) for immunogenicity testing.
Note: blood samples for immunogenicity will be drawn in Phase 2 maternal participants only.
- Obtain a nasal swab (collected by site staff).
- Unblinded site staff member(s) will dispense/administer 1 dose of study intervention into the deltoid muscle of the (preferably) nondominant arm. Please refer to the IP manual for further instruction on this process.

- Blinded site staff must observe the participant for at least 30 minutes after study intervention administration for any acute reactions. Record any acute reactions (including time of onset) in the participant's source documents and on the AE page of the CRF, and on an SAE form as applicable.
- Ask the participant to contact the site staff or investigator if the participant experiences acute chest pain, shortness of breath, or palpitations (see [Section 8.14](#)).

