6.2.1.2.1. Main Analyses

- Estimand:
 - $100 \times (1 - \text{IRR})$ [ratio of incidence of asymptomatic infection of SARS-CoV-2 through 1 month after delivery in evaluable maternal participants without evidence of prior SARS-CoV-2 infection for the active vaccine group to the placebo group ([Section 2.1](#))].
- Analysis set: Evaluable efficacy population (maternal), all-available efficacy population (maternal) ([Section 4](#)).
- Analysis time point: End of the surveillance period.
- Analysis methodology: Assessment of VE will be performed for the incidence of asymptomatic infection of SARS-CoV-2 through 1 month after delivery, and will be estimated by $100 \times (1 - \text{IRR})$, where IRR is the calculated ratio of incidence of asymptomatic infection per 1000 person-years of follow-up in the active vaccine group to the corresponding infection rate in the placebo group through 1 month after delivery (see [Appendix 2](#) for details on the definition of asymptomatic infection and the derivation of IRR and VE).
- Intercurrent events and missing data: Missing N-binding data will not be imputed.

- Reporting results: VE and the associated 2-sided 95% CI derived using the Clopper-Pearson method adjusted for surveillance time will be provided.

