2. The flowchart for deriving the COVID-19 cases included below for the second VE endpoint in evaluable efficacy participants:

Asymptomatic Case Definition

An asymptomatic case is defined as positive N-binding antibody at a post-Dose 2 visit (eg, Visit 4, 1 month after Dose 2) in participants without serological or virological evidence of infection prior to that visit, determined by negative N-binding antibody at Visit 1 and negative NAAT at Visit 1 and Visit 2 and at the time of a potential COVID-19 illness. A secondary definition will be applied without the requirement for a negative NAAT at Visit 2.

Surveillance Times

For the asymptomatic cases based on N-binding antibody seroconversion, the start-of-surveillance times are summarized as follows:

Endpoint's Associated Participant-Level Population	Start-of-Surveillance Time
Evaluable efficacy (maternal)	Dose 2
Dose 2 all-available efficacy (maternal)	Dose 2
Dose 1 all-available efficacy (mITT) (maternal)	Dose 1

The end of a surveillance period for each participant is the earliest of the following:

- Date of the first positive N-binding antibody result after Dose 2.
- Date of the participant's last post-Dose 2 N-binding antibody test that is prior to a COVID-19 symptom associated with a nonnegative NAAT result.
- Date of the participant's last post-Dose 2 N-binding antibody test that is prior to an important protocol violation (for analysis based on the evaluable efficacy population).

Once the asymptomatic cases and surveillance periods have been identified, VE can be calculated as $100 \times (1 - \text{IRR})$, where IRR is the ratio of incidence of asymptomatic infection per 1000 person-years of follow-up for the active vaccine group to the placebo group.

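### In the two sets whose clock starts at Dose 2, asymptomatic infections acquired between the doses can count as post-Dose 2 cases, because N-binding negativity is required only at Visit 1

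*SAP*

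**What the plan says.** SAP Appendix 2 (Asymptomatic Case Definition) takes as a case a positive N-binding result at a visit after Dose 2 in a woman with no prior evidence of infection. That absence is "determined by negative N-binding antibody at Visit 1 and negative NAAT at Visit 1 and Visit 2", plus a negative NAAT at any potential COVID-19 illness. The SAP adds: "A secondary definition will be applied without the requirement for a negative NAAT at Visit 2".

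The Surveillance Times table that follows starts the asymptomatic clock at Dose 2 for the evaluable efficacy and Dose 2 all-available sets, and at Dose 1 for the Dose 1 all-available (mITT) set. For a case, the clock stops at the "Date of the first positive N-binding antibody result after Dose 2". SAP 6.2.1.2.1 analyses the endpoint in the evaluable and all-available efficacy sets, as VE with a 2-sided 95% CI adjusted for surveillance time.

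On sampling at Visit 2, a footnote to the schedule of activities (Protocol 1.3.1) says: "Prevaccination blood samples for immunogenicity will be drawn from maternal participants in Phase 2 only". Protocol 8.11.1.1 repeats the restriction. Protocol 8.1.3 lists the N-binding assay among those to be run on sera from the scheduled visits.

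**The concern.** In the two sets that start at Dose 2, the last serology that must be negative precedes Dose 1. A woman infected without symptoms a few days after Dose 1 may be NAAT-negative again by Visit 2. She has no illness visit, so no NAAT is taken in between. She is first found N-positive after Dose 2 and counts as a post-Dose 2 case, while her time at risk between the doses is not counted.

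The plan is stricter for symptomatic disease in women without prior infection. There, evidence of infection up to 7 days after Dose 2 excludes the woman, and the clock starts at that same point (SAP 3.2.1 and Appendix 2). The asymptomatic endpoint has no matching safeguard.

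At stake is what the reported VE means. Part of it would describe protection between the doses while being read as protection after two doses. The evaluable set is affected, and SAP 2.1 bases the efficacy estimands on it.

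**Working it through.** The plan states no event count, rate or expected VE for this endpoint, so there is no figure to reproduce. The nearest is 95.0% for symptomatic disease in C4591001 (Protocol 2.2.1), which agrees with its counts: 1 - 8/162 = 95.1% if person-time is equal.

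**Inputs from the documents**
- Dose interval G: 21 days (scheduled 19-23; the evaluable efficacy set allows 19-42).
- Dose 1 at 24 to 34 weeks' gestation; 1:1 randomization.

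**Assumptions**
- Constant hazard, and equal follow-up in the two arms. The Visit 101 blood sample, scheduled for placebo recipients only, is left aside.
- Delivery at 40 weeks. Dose 2 to delivery is then 40 - 34 - 3 = 3 weeks to 40 - 24 - 3 = 13 weeks, that is 21-91 days, with midpoint T = 56.
- NAAT stays positive for d days: 7-14 under the primary definition. The secondary definition is represented by d = 0.
- Infection to N-seroconversion takes s days: 0 or 10.
- Post-Dose 2 VE v2 = 0.95, borrowed from symptomatic disease; 0.60 is also tried.
- Inter-dose VE v1 between 0 and v2. The documents give no figure for it.

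**Formulas**
- Inter-dose days whose infections pass the Visit 2 check: w = G - d.
- Placebo rate factor: (w + T - s)/T.
- Observed VE: 1 - [(1 - v1)w + (1 - v2)(T - s)]/(w + T - s).

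**VE at T = 56, s = 0, v2 = 0.95**

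| Definition | w | v1 = 0 | v1 = 0.5 | v1 = v2 |
|---|---|---|---|---|
| Primary, d = 10 | 11 | 1 - (11 + 2.8)/67 = 79.4% | 1 - (5.5 + 2.8)/67 = 87.6% | 95.0% |
| Secondary | 21 | 1 - (21 + 2.8)/77 = 69.1% | 1 - (10.5 + 2.8)/77 = 82.7% | 95.0% |

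With v2 = 0.60, the primary definition (d = 10) gives 50.1%, 58.4% and 60.0%.

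**Placebo rate factor, s = 0**

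| | T = 21 | T = 56 | T = 91 |
|---|---|---|---|
| Primary, d = 14 to 7 | 1.33-1.67 | 1.12-1.25 | 1.08-1.15 |
| Secondary | 2.00 | 1.38 | 1.23 |

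**With a 10-day lag, T = 56.** Infections late in follow-up are missed, and the primary factor falls to (7 + 46)/56 = 0.95 for d = 14 and (14 + 46)/56 = 1.07 for d = 7. The rate may then not be overstated at all. VE is still diluted: for d = 10 and v1 = 0 it is 1 - (11 + 2.3)/57 = 76.7%.

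**Long NAAT positivity.** If d = 21, then w = 0 and the effect vanishes under the primary definition.

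**Dose 1 all-available set, s = 0.** The factor is (w + T)/(G + T): 1.00 under the secondary definition and 0.67-0.94 under the primary (d = 7-14, T = 21-91). Its rate is not overstated.

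**Where the VE shift comes from.** The VE formula contains no time origin. With equal allocation and follow-up, the person-time ratio between arms is close to 1 whether the clock starts at Dose 1 or Dose 2. The shift comes from the admitted cases.

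**The case against.** Five arguments can be made for the plan.

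- *The definition already excludes anyone with earlier evidence of infection.* The clause that follows names the tests that decide this, and Visit 2 serology is not among them. Even on the generous reading, Phase 3 has no Visit 2 serum to check.
- *The estimand for this endpoint names no start of risk, so inter-dose infections may be intended.* It does run only through 1 month after delivery. But Appendix 2 then starts the clock at Dose 2 in two of the three sets, so the two parts still need to be aligned.
- *An analysis from Dose 1 is already planned.* This stands. A reader might infer that the whole endpoint is affected; the Surveillance Times table does not support that.
- *The Visit 2 NAAT removes some inter-dose infections.* This also stands. Under the primary definition the numerator does not reach back over the full interval; only infections cleared or undetected by Visit 2 get through. The larger effects belong to the secondary definition.
- *The endpoint is secondary and descriptive.* True. No hypothesis test, alpha or power depends on it, and Protocol 4.2 expects a minimal number of cases. With few cases, though, one or two misattributed ones could move the estimate.

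**Conclusion.** The mismatch holds for the evaluable efficacy and Dose 2 all-available sets. It can inflate their rates, and it pulls VE toward inter-dose efficacy. For the illustrated case (56 days, 95% after Dose 2, 0-50% between doses), VE would read about 79-88% under the primary definition with 10-day NAAT positivity and 69-83% under the secondary. These figures rest on the assumptions listed and do not predict the trial's result.

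Three stronger readings are tempting, and the documents do not support them:

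- **Rates are necessarily overstated.** Seroconversion lag can offset the inflation partly or fully.
- **VE is necessarily diluted.** That needs inter-dose efficacy below post-Dose 2 efficacy. This is plausible, but the documents give no figure, and with equal efficacies VE is unchanged.
- **The late clock causes the dilution, so an earlier start would repair VE.** It would change the rate and leave essentially the same cases in the ratio.

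**What to change.** In SAP Appendix 2, for the two sets that start at Dose 2:

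1. Where a Visit 2 (pre-Dose 2) sample is drawn, which means Phase 2 (about 200 women), also require a negative N-binding result on it. Report that Phase 2 estimate as the post-Dose 2 VE.
2. Report Phase 3 (about 150 women) separately, and label its VE as including some inter-dose infections. Describe any Dose 1-origin rate as matching numerator and denominator under the secondary definition only (under the primary it can understate the rate), and as not repairing VE.
3. Keep the current derivation as a sensitivity analysis.

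In the illustration with no lag, step 1 sets w = 0 and observed VE equals v2. With a lag, the residual is s - d days where positive: none for s = d = 10, 3 days for s = 10 and d = 7, and 10 days under the secondary definition with s = 10. The primary definition is therefore the better basis for the Phase 2 estimate.

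The cost is SAP wording, a derivation change and use of N-binding results on Visit 2 serum that is already scheduled; no new blood is needed. The clean estimate rests on fewer women, and there are two results to explain.

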7. DISCONTINUATION OF STUDY INTERVENTION AND PARTICIPANT DISCONTINUATION/WITHDRAWAL

7.1. Discontinuation of Study Intervention

In rare instances, it may be necessary for a participant to permanently discontinue study intervention (definitive discontinuation). Reasons for definitive discontinuation of study intervention include the following: AEs; participant request; investigator request; protocol deviation (including no longer meeting all the inclusion criteria, or meeting 1 or more exclusion criteria). In general, unless the investigator considers it unsafe to administer the second dose, or the maternal participant does not wish to receive it, it is preferred that the second dose be administered. Note: following Vaccination 1, a positive SARS-CoV-2 NAAT result without symptoms or a COVID-19 diagnosis (signs/symptoms only or signs/symptoms and a positive SARS-CoV-2 NAAT result) should not result in discontinuation from the study intervention.

Note that discontinuation of study intervention does not represent withdrawal from the study. Per the study estimands if study intervention is definitively discontinued, the participant will remain in the study to be evaluated for safety, tolerability, and immunogenicity. See the [SoA](#) for data to be collected at the time of discontinuation of study intervention and follow-up for any further evaluations that need to be completed.

In the event of discontinuation of study intervention, it must be documented on the appropriate CRF/in the medical records whether the participant is discontinuing further receipt of study intervention or also from study procedures, postvaccination study follow-up, and/or future collection of additional information.

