All-available efficacy (mITT) (maternal)	Dose 1 all-available efficacy: All randomized participants who receive at least 1 vaccination. Dose 2 all-available efficacy: All randomized participants who complete 2 vaccination doses.

Population	Description
All-available efficacy (mITT) (infant)	All infant participants born to Dose 1 all-available maternal participants.
Safety (maternal)	All randomized participants who receive at least 1 dose of the study intervention.
Safety (infant)	All infant participants born to maternal participants who receive at least 1 dose of the study intervention.

The important protocol deviations will be determined by the medical monitor. An important protocol deviation is a protocol deviation that, in the opinion of the sponsor's clinician, would materially affect assessment of immunogenicity/efficacy, eg, participant receipt of a prohibited vaccine or medication that might affect immune response or a medication error with suspected decrease in potency of the vaccine. The sponsor's clinician will identify those participants with important protocol deviations that result in exclusion from analysis populations before any unblinded analysis is carried out.

For all the immunogenicity endpoints, the analysis will be based on the evaluable immunogenicity population. An additional analysis will be performed based on the corresponding all-available immunogenicity population if there is over 10% difference in sample size between the all-available immunogenicity population and the evaluable immunogenicity population. Participants will be summarized according to the vaccine group to which the maternal participants were randomized.

The safety analyses will be based on the safety population. Participants will be summarized by vaccine group according to the study interventions the maternal participants actually received.

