5.1. Hypotheses and Decision Rules

Due to early enrollment termination and reduced sample size, all endpoints will be analyzed descriptively without formal hypothesis tests.

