5.2. General Methods

Unless specified otherwise, “vaccine group” in this document is based on the study intervention (BNT162b2 or placebo) to which the maternal participants are randomized or that they receive. The vaccine group of the infant participants will follow the vaccine group of their mothers. CIs for all endpoints in the statistical analysis will be presented as 2-sided at the 95% level unless otherwise specified.

Missing reactogenicity e-diary data will not be imputed; missing start AE dates will be handled according to the Pfizer safety rules.

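### For the Dose 1 all-available set, the asymptomatic-infection clock starts at Dose 1, but the primary case rule drops infections NAAT-positive at Visit 2 and ignores women with no post-Dose 2 N test

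*SAP*

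**What the plan says.** SAP Section 6.2.1.2 estimates VE against asymptomatic infection as 100 × (1 − IRR), in the evaluable efficacy population and in an all-available efficacy population. It does not say which of the two all-available sets is meant. SAP Appendix 2 has a row for each.

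- **Who is in the set.** SAP Section 4: "Dose 1 all-available efficacy: All randomized participants who receive at least 1 vaccination". Dose 2 is not required.
- **When the clock starts.** The asymptomatic surveillance table in Appendix 2 gives Dose 1 for this set and Dose 2 for the other two.
- **What counts as a case.** One definition serves all three sets: "An asymptomatic case is defined as positive N-binding antibody at a post-Dose 2 visit", in women without earlier infection, "determined by negative N-binding antibody at Visit 1 and negative NAAT at Visit 1 and Visit 2" and at any potential COVID-19 illness. The next sentence adds a secondary definition that drops the Visit 2 NAAT condition.
- **When the clock stops.** The list opens with "Date of the first positive N-binding antibody result after Dose 2". The other two end dates are also dates of N tests done after Dose 2.
- **What happens to women who stop after one dose.** Protocol Section 7.1: "the participant will remain in the study to be evaluated for safety, tolerability, and immunogenicity". The schedule in Protocol Section 1.3.1 includes a blood draw at delivery.

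**The concern.** In this set, the period in which a woman is counted as at risk differs from the period in which she can become a case. There are two separate consequences.

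1. A woman who is N-negative and NAAT-negative at Visit 1 and NAAT-positive without symptoms at Visit 2 has a documented new infection after her clock started. The primary definition treats it as evidence of earlier infection, so she cannot be a case. Protocol Section 8.16 foresees such women and has them proceed to Vaccination 2.
2. A woman who receives only Dose 1, or who has no N sample after Dose 2, belongs to the set but can never be a case. Her person-time cannot be calculated from the text as written.

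The purpose of the Dose 1 set is to describe efficacy from first vaccination. If protection is weaker before Dose 2, dropping some of the between-dose infections moves the estimate towards the efficacy seen after Dose 2, and the set no longer measures what its definition says.

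**Working it through.** **Plan's own figure.** The documents give no expected rate, count or VE for asymptomatic infection, so there is nothing to reproduce for this endpoint. As a check of the formula, Protocol Section 2.2.1 reports 8 against 162 cases under 1:1 allocation in the earlier trial: 100 × (1 − 8/162) = 95.1%, against the stated 95.0%.

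**First consequence: infections NAAT-positive at Visit 2.**

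Inputs from the documents: G = 21 days between doses; vaccination at 24 to 34 weeks' gestation; 1:1 allocation of about 350 women, so about 175 per arm.

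Assumed inputs:
- gestational age uniform over 24 to 34 weeks, delivery at 40 weeks, last N test at delivery;
- placebo attack rate 5 to 10% per 70 days;
- NAAT positivity lasting 7 to 14 days;
- VE after Dose 2 (VE2) 50 to 90%, and VE between doses (VE1) 0 or 30%.

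Time from Dose 1 to delivery runs from (40 − 24) × 7 = 112 days to (40 − 34) × 7 = 42 days, mean 77. The mean time after Dose 2 is F = 77 − 21 = 56 days. The share q of between-dose infections still NAAT-positive at Visit 2 is 7/21 = 1/3 to 14/21 = 2/3.

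At low attack rates, placebo cases are proportional to G(1 − q) + F and vaccine cases to (1 − VE1)G(1 − q) + (1 − VE2)F. Person-time is the same in both arms and cancels. Hence:

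- all infections after Dose 1 counted: VE = (VE1·G + VE2·F) / (G + F);
- primary definition: VE = (VE1·G(1 − q) + VE2·F) / (G(1 − q) + F);
- difference = (VE2 − VE1)·F·G·q / [(G + F)(G(1 − q) + F)].

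The sign of the difference is the sign of VE2 − VE1.

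| VE1 | VE2 | q | All counted | Primary definition | Shift (points) |
|---|---|---|---|---|---|
| 0 | 50% | 1/3 | 28.0/77 = 36.4% | 28.0/70 = 40.0% | +3.6 |
| 0 | 90% | 2/3 | 50.4/77 = 65.5% | 50.4/63 = 80.0% | +14.5 |
| 30% | 50% | 1/3 | 34.3/77 = 44.5% | 32.2/70 = 46.0% | +1.5 |
| 30% | 90% | 2/3 | 56.7/77 = 73.6% | 52.5/63 = 83.3% | +9.7 |
| 60% | 60% | any | 60.0% | 60.0% | 0 |
| 60% | 40% | 1/3 | 35.0/77 = 45.5% | 30.8/70 = 44.0% | −1.5 |

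Averaging over the gestational-age range, and letting infection deplete those at risk at the assumed attack rates, gives +3.6 to +15 points with VE1 = 0 and +1.4 to +10 points with VE1 = 30%. The placebo rate falls by about 7/77 = 9% to 14/77 = 18% on the simple formula, and by 9 to 19% with depletion.

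In cases per placebo arm: between-dose infections number about 175 × 0.05 × 21/70 = 2.6 to 175 × 0.10 × 21/70 = 5.3. The rule removes one-third to two-thirds of them, about 0.9 to 3.5.

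**Second consequence: no N test after Dose 2.** No arithmetic applies. SAP Section 4 admits a one-dose woman to the set, Protocol Section 7.1 keeps her in the study, and a delivery sample is scheduled. The case definition and every end date in Appendix 2 need a result after Dose 2, which she cannot have. Nothing in the text gives her an end of person-time. A two-dose woman with no later N result is in the same position. Protocol Section 1.3.1 makes this possible, because Visits 3 and 4 are skipped if delivery comes first and Dose 2 may itself follow delivery.

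**The case against.** The strongest reply is that the SAP already plans the remedy for the first consequence. The secondary definition sets q = 0, so every shift in the table is the difference between two analyses that will both be available. That is correct. But the secondary definition is not the leading one for this set, and it does nothing about the required post-Dose 2 test or the missing end date.

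A reader might infer that all between-dose infections are removed, making the first 21 days event-free (immortal) time. The text does not support that. N is not required to be negative at Visit 2, so a woman infected between doses who is NAAT-negative by Visit 2 becomes a case at her next positive N test. On the assumptions above, one-third to two-thirds of between-dose infections are kept. Nor does the added person-time bias the ratio by itself: under 1:1 allocation it enters both arms about equally (175 × 21/365.25 = 10.1 person-years per arm) and cancels. Only lost cases matter.

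The second consequence may affect few women. The protocol prefers that Dose 2 be given, gives it as soon as possible after an early delivery, and does not stop it for a positive NAAT or COVID-19. Appendix 2 also leaves detailed start and end times by VE endpoint to specification documents that are not available here. They might supply an end date, but the asymptomatic rules already printed cannot be applied to part of the set.

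Precision will be poor: 5 against 10 cases gives VE 50% with a 95% interval of about −61 to 87%, and 9 against 18 gives about −17 to 80%. SAP Section 5.1 states that "all endpoints will be analyzed descriptively without formal hypothesis tests", and the objective's estimand is in evaluable participants. This limits the weight of the point but does not remove the mismatch.

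**Conclusion.** The mismatch is real and is confined to the Dose 1 all-available row. The primary definition discards infections that are NAAT-positive at Visit 2 although they fall within surveillance. Women without a post-Dose 2 N test can never be cases and have no end date; that part rests on no assumption about efficacy, but its size is unknown.

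It would be tempting to conclude that VE in this set is overstated. The documents do not establish that. Protocol Section 2.2.1 says immunogenicity rose substantially after the second dose, which makes weaker protection between doses plausible, but no between-dose efficacy is given. If protection is weaker between doses, the overstatement is about 3.6 to 15 points with none and 1.4 to 10 points with 30%, on the assumed gestational-age distribution, attack rate, NAAT duration and post-Dose 2 efficacy. It is zero if protection is equal in the two periods, and the shift is downward if protection is stronger between doses.

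This is a worthwhile correction to a descriptive supporting analysis.

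**What to change.** In SAP Appendix 2, add a rule for the Dose 1 all-available row of the asymptomatic endpoint only:

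- make the existing secondary definition, without the Visit 2 NAAT condition, the leading one for this set;
- count the first positive N result at any visit after Dose 1, including the pre-Dose 2 sample in Phase 2 and the delivery sample of women who received one dose;
- end person-time at that date, or otherwise at the last N test after Dose 1, keeping the present censoring at a COVID-19 symptom with a nonnegative NAAT.

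Leave the two rows that start at Dose 2 unchanged.

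The cost is a few lines of SAP text and a small programming change. The samples are already scheduled and the N-binding assay is already planned (Protocol Section 8.1.3). The downside is that VE in this set may look less favourable, because it would then include more of the infections acquired between doses.
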